### **4) Blinding:**

The operator will be blinded to material and assessors H.M. & E.M. will be blinded to the material assignment.

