## 2) Participant timeline: (Table 2)

Activity	Staff member	T0 Baseline	T1 After 5 min	T2 After 15 days
Recruitment	Y.S.	X		
Diagnosis	Y.S.	X		
Consent	Y.S.	X		
Baseline data collection	Y.S.	X		
Randomization	Y.S.	X		
Saliva & Plaque sampling	M.A.	X	X	X
Outcome assessment	H.M. E.M.	X	X	X

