### **B) Assignment of interventions (Allocation):**

#### **1) Sequence generation:**

Simple randomization will be done by generating numbers from 1:98 using Random Sequence Generator, Randomness and Integrity Services Ltd (<https://www.random.org/>) by Y.S. Each generated random number will represent assigning intervention and comparator in a random manner, i.e.: No. 1 intervention No.2 comparator.

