#### **2) Allocation concealment:**

Operator M.A. will choose between numbers in an opaque sealed envelope, which will be arranged by Y.S. who will not be involved in any of the phases of the clinical trial. Data will be recorded on a computer by M.A. and H.M. and all records of all patients will be kept with the main supervisor A.E.

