### **3) Implementation:**

Y.S. will generate the allocation sequence, enroll participants, and assign participants to interventions.

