#### **5) Access to data:**

Access to final data will be allowed to M.A. and the main and co-supervisors (A.E., A.H. & O.S.) who are not involved in assessment of the outcome.

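### The operator is declared blinded, yet draws the allocation number and samples patients immediately before and 5 minutes after visibly different products

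*Protocol*

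**What the plan says.** Protocol III.B 4) Blinding covers the operator and the two assessors in one sentence: "The operator will be blinded to material", and the assessors likewise to the assignment. Four other places bear on the operator.

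- **III.B 1) Sequence generation** lets each number stand for an arm: "No. 1 intervention No.2 comparator".
- **III.B 2) Allocation concealment** says that the operator "will choose between numbers in an opaque sealed envelope". The envelopes are prepared by the person who generates the sequence, and that person is described as having no part in any phase of the trial.
- **III.B 3) Implementation** gives the allocation steps to that same person, who "will generate the allocation sequence, enroll participants, and assign participants to interventions".
- **Participant timeline (Table 2)** assigns the row "Saliva & Plaque sampling" to the operator at T0, at T1 (5 minutes) and at T2 (15 days). Randomization is also placed at T0.

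III.A 3) Interventions defines T0 as before either product is taken. It has the gum chewed for 5 minutes, and the tablet chewed, swished round the mouth and swallowed.

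**The concern.** A person who draws the number that denotes the arm, and who is with the patient shortly before and shortly after the product is used, would ordinarily know which product it was. The operator's knowledge matters because the operator produces the samples on which every outcome rests.

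Plaque is the most exposed. It is scraped by hand from the surfaces between the teeth and dispersed in water, and the protocol fixes no weight, number of sites or volume of water. A sampler who knows the arm could scrape more in one arm than in the other without intending to. Counting the plates blind does not undo this, because the difference is already in the tube.

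Reporting is also at stake: a trial report that repeats the Blinding section would claim a blinded sampler that the procedures do not deliver.

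**Working it through.** The protocol gives no figure to reproduce. The check sets the statements side by side.

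**1. Drawing the number.** Allocation concealment has the operator draw it, and Sequence generation makes the number stand for the arm. Read together, the operator learns the arm. Implementation has someone else assign participants. Both cannot describe the same step, so this evidence alone leaves room for doubt.

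**2. Sampling around product use.** This does not depend on step 1. Assume the T0 sample is taken just before the product, since the protocol states no gap. The protocol does not say whether the 5 minutes to T1 run from the start or the end of use, so take both readings for gum, which is chewed for 5 minutes:

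- from the start of use: T1 is 5 − 5 = 0 minutes after chewing ends;
- from the end of use: T1 is 5 + 5 = 10 minutes after chewing began.

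So the operator samples, a product is used, and the operator samples again 5 to 10 minutes after use of the gum began. The tablet is swallowed and the gum is not, so the two look different in use. The protocol describes no placebo, no masking, no separate person handing over the product and no rule keeping the operator away meanwhile. Patients are not listed among those blinded, so they may also tell the operator what they took.

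**3. Route from the sampler to the result.** For plaque, with *d* bacteria per mg, *m* mg scraped and *V* ml of water,

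CFU/ml = *d* × *m* / *V*.

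With *d* and *V* equal in the two arms, the ratio of counts equals *m*₁/*m*₂, and the shift is log10(*m*₁/*m*₂). The amount scraped therefore passes through in full. The classes in Table 1 (10², 10³, 10⁴, 10⁵) lie one log10 apart, so moving a whole distribution by one class needs log10(*m*₁/*m*₂) = 1, a tenfold difference. A sample near a class boundary would move with much less. The protocol gives no plaque weights and no spread of counts, so neither the likely ratio nor the proportion near a boundary can be estimated.

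Saliva, the primary outcome, is counted per ml of fluid. A larger volume does not by itself raise a concentration, so this route does not carry over to it.

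**4. Assessors.** The sections say three things:

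- Allocation concealment: "Data will be recorded on a computer by" the operator and one assessor.
- III.C 2) Data management: the other assessor checks the operator's entries.
- III.A 3) Interventions: colonies are counted by one examiner who does not know the treatment. III.D 1) Data monitoring has the main supervisor watch over assessor blinding.

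No section says that the data file holds the allocation. The statements are compatible with blinded assessors, but the protocol does not describe coded tubes or a separate allocation list.

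**The case against.** The best defence is that the operator may draw only a coded number without learning its meaning, that Implementation has another person assign, and that no section places the operator at the bedside during chewing. Unblinding would then be likely but not stated. This weakens the envelope evidence. It does not remove the sampling evidence, because nothing in the protocol keeps the operator away for those few minutes or hides the product.

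It may also be said that plate counts and pH-meter readings are objective. That is fair for the reading of samples but not for the taking of plaque.

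Two stronger readings are tempting and should not be drawn.

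- **That assessor blinding fails as well**, since both assessors handle data. Recording or checking outcome data unblinds nobody unless the arm is in the file, and the protocol does not say that it is. It also provides for blind counting and for monitoring of assessor blinding.
- **That IV 5) Access to data is contradicted**, because it calls those with access people "who are not involved in assessment of the outcome". That section concerns final data and lists the operator and the supervisors, none of whom is a named assessor. It is consistent with the stated roles.

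**Conclusion.** The claim that the operator is blinded is contradicted by the protocol's own procedures and should not stand. The conclusion rests on the T0 and T1 sampling by one person around two visibly different products, and assumes that no unstated masking or separation is in place. The drawing of the number adds to it, and the conflict between Allocation concealment and Implementation over who allocates must be resolved in any case.

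The consequence is confined mainly to the interdental plaque count, and its size cannot be given from the document. No clear route to the salivary *S. mutans* count was found. Assessor blinding is stated and uncontradicted. It needs protection because the assessors share data handling with an operator who in effect knows the arm.

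**What to change.** 1. Reconcile Allocation concealment with Implementation. Let the team member who already assigns participants, and who is neither operator nor assessor, hold the envelopes and hand over the product. Correct the statement that this person has no part in any phase: Implementation, Table 2, Baseline data collection and Consent all give that person tasks. (This settles who knows the arm at sampling. It does not address the separate matter of one person both generating the sequence and enrolling.)
2. State that the operator enters only after product use is finished and the product has been removed.
3. If 1 and 2 are not adopted, delete the claim that the operator is blinded and report the sampler as unblinded.
4. Label tubes with study codes only, and keep allocation out of the outcome file until all plates are read.

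The cost is a reassignment of existing roles, coded labels and a few edited sentences. No extra staff, visits or samples are needed.

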## **C) Data collection, management, and analysis:**

### **1) Data collection methods:**

#### **1.1. Baseline data collection:**

For every patient medical and dental history will be taken. Examination charts will be filled by Y.S.

#### **1.2. Outcome data collection:**

Outcomes will be evaluated by two assessors H.M. & E.M. before interventions, after 5 minutes and 15 days, if both assessors differ in score, they will discuss, if did not agree a third assessor will resolve the conflict.

#### **1.3. Patient retention:**

The phone number of the patient or his/her caregiver will be recorded in the patient's chart. The patient will receive a phone call by Y.S. to remind him of the time of the operator M.A. visit for saliva and plaque sampling. Moreover, patients will receive a daily phone message in the time assigned for chewing either the gum or the tablet.

### **2) Data management:**

Data entry will be accomplished by M.A. & revised by E.M. All data will be stored on computer and will be encrypted using a password. This is

done to allow accurate data entry thorough revision and protect data from being inadvertently used. Data will be backed up on another computer to prevent it from being lost.

### **3) Statistical methods:**

Data will be analyzed using IBM SPSS advanced statistics (Statistical Package for Social Sciences), version 25 (SPSS Inc., Chicago, IL). Categorical data will be described as absolute risk for each intervention independently and relative risk when comparing both interventions. Comparisons between categorical variables will be performed using the chi square test and Kruskal Wallis will be used to test interaction of variables. Continuous data will be described using mean and standard deviation. Comparison between continuous data will be performed using t-test and two-way ANOVA will be used to test interaction of variables. A p-value less than or equal to 0.05 will be considered statistically significant and all tests will be two tailed.

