### 1) Outcomes: (*Table 1*)

No.	Outcome Name	score	Criteria	type	Methods of aggregation
1ry	Salivary S.mutans count	VL: very low	10  cfu/ml	Categorical ordinal	Absolute risk will be reported for each intervention independently. Relative risk will be used to compare both interventions with 95 % CI.
		L: low	10  cfu/ml		
M: Moderate	10  cfu/ml				
H: High	10  cfu/ml				
2ry	Interdental plaque Bacterial count	Swapnil et al, 2018			
3ry	Salivary ph	Numerical values	Normal salivary ph = 6.2 - 7.6	Continous	Mean and Standard deviation
		Baliga et al, 2013			

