## 3) Sample size calculation:

A power analysis was designed to have adequate power to apply statistical test of the research hypothesis that dissolving xylitol chewing tablets will have the better antibacterial effect than xylitol chewing gum against mutans streptococci after 1 month. According to the results of *Swapnil et al. in 2018* in which the probability of bacterial count reduction to  $10^2$  for xylitol chewing gum (comparator) was (0.15), probability of bacterial count reduction to  $10^3$  was (0.6) and probability of bacterial count reduction to  $10^4$  was (0.25) with effect size  $w=0.578$  ( $n=29$ ). If the estimated probability of dissolving xylitol chewing tablets for bacterial count reduction to  $10^2$  is (0.35), probability of bacterial count reduction to  $10^3$  is (0.5) and probability of bacterial count

reduction to  $10^4$  was (0.15) with effect size  $w=0.43$  ( $n=53$ ). By adopting an alpha ( $\alpha$ ) level of 0.05 (5%), power=80%. The predicted sample size ( $n$ ) was a total of (82). Sample size was increased by (20%) to account for possible dropouts during follow-up intervals to be total of (98) cases i.e. (49) for each group. Sample size calculation was performed using G\*Power 3.1.9.2.

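### Kruskal-Wallis is assigned to test interaction, which a one-way rank test cannot do; a lesser point is that the ordinal primary grade is compared between arms by a chi-square that ignores order

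*Protocol*

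**What the plan says.** The Statistical methods section (III.C) gives the rule for categorical outcomes in one sentence: "Comparisons between categorical variables will be performed using the chi square test and Kruskal Wallis will be used to test interaction of variables". It does not say which variables might interact. The matching sentence for continuous data gives comparison to the t-test and interaction to two-way ANOVA. All tests are two-sided at 0.05.

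Table 1 (Outcomes, III.A) types the primary outcome, the salivary S. mutans grade, as "Categorical ordinal", with four levels from very low to high. The grade is scored "before interventions, after 5 minutes and 15 days, if both assessors differ in score", so each patient contributes three readings.

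The Sample size section states a directional research hypothesis, that "dissolving xylitol chewing tablets will have the better antibacterial effect than xylitol chewing gum". It plans on gum proportions of 0.15/0.60/0.25 and tablet proportions of 0.35/0.50/0.15 for grades 10^2/10^3/10^4. No section assigns an order-using test to the comparison of arms.

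**The concern.** Two-way ANOVA has an interaction term, and the parallel wording suggests that Kruskal-Wallis was meant as its counterpart for categorical data. It is not one. It asks whether several independent groups share one distribution, so any difference among them can make it significant. A significant result could then be written up as an arm-by-visit interaction when both arms merely changed alike over time.

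The second point is smaller. The chi-square gives the same answer however the grades are rearranged. It therefore gives up some power against the planned shift to lower grades, and its significance need not mean such a shift.

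**Working it through.** **Inputs.** From the Sample size section: gum 0.15/0.60/0.25, tablet 0.35/0.50/0.15, 82 patients before dropout (41 per arm) and 98 after (49 per arm). These three proportions sum to 1 in each arm, so the fourth grade in Table 1 (high) is taken as zero. Assumed: a within-patient correlation of 0.3 to 0.7, and the starting distributions given below.

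**The plan's own figure.** The stated 82 is 29 + 53. It reproduces if each arm is tested alone against equal thirds (2 df, 80% power):
- Gum: w = √(3 × [0.1833² + 0.2667² + 0.0833²]) = 0.579, n = 29.
- Tablet: w = √(3 × [0.0167² + 0.1667² + 0.1833²]) = 0.430, n = 53.

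The figure is therefore not the power of a between-arm test. That is a separate sample-size matter.

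**Kruskal-Wallis as an interaction test.**
- Two arms only: it is identical to Mann-Whitney, a test of the arm effect.
- Six cells (two arms by three visits), latent normal grades, same distribution in both arms, T0 and T1 alike, then a move to 0.15/0.60/0.25 at T2. There is neither an arm effect nor an interaction. From an assumed start of 0.10/0.55/0.35 it rejects in about 13–23% of trials. From 0.05/0.50/0.45 it rejects in about 80–92%.
- Four cells (two arms by T1 and T2), with the planned arm difference equal at both visits and so no interaction: it rejects in about 57–72%.
- Six cells with no effect at all: about 3–4%. The false signals above therefore come from the main effects. Ignoring the within-patient correlation by itself makes the test slightly conservative here.

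**Chi-square against a rank test.**
- Pooled proportions are 0.25/0.55/0.20. Chi-square: w² = 0.10²/0.25 + 0.05²/0.55 + 0.05²/0.20 = 0.0570. The noncentrality is 82 × 0.0570 = 4.68 or 98 × 0.0570 = 5.59 on 2 df, giving power of 48% and 55%. Simulation gives 48–49% and 56%.
- Rank test: P(tablet lower) = 0.35 × 0.85 + 0.50 × 0.25 = 0.4225. P(tie) = 0.35 × 0.15 + 0.50 × 0.60 + 0.15 × 0.25 = 0.39. So P = 0.4225 + 0.195 = 0.6175.
- The tie factor is 1 − (0.25³ + 0.55³ + 0.20³) = 0.81. Power = Φ(√[3N(P − 0.5)²/0.81] − 1.96), which is 53% at N = 82 and 61% at N = 98. Simulation gives 54% and 62%.
- With no arm difference, both tests reject in about 5% of trials.

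**Order, with illustrative counts.** Take gum 7/30/12 and tablet 17/25/7. The chi-square is 5.94 (p = 0.051), and stays so when the first two grades are swapped. The rank statistic is 5.30 (p = 0.021) in the true order and 0.13 (p = 0.72) after the swap.

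**When order hurts.** Take an illustrative tablet result of 0.30/0.40/0.30 at 41 per arm. Chi-square power is 41% and rank-test power is 9%. Here P(lower) = 0.30 × 0.85 + 0.40 × 0.25 = 0.355 and P(tie) = 0.045 + 0.24 + 0.075 = 0.36, so P(lower) + ½P(tie) = 0.535.

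**The case against.** No stated objective or outcome is an interaction, so the mislabelled test leaves the primary between-arm result untouched. That stands, and it limits the harm to whatever is reported as an interaction. The six-cell layout is also only one reading, because the protocol names no variables. That stands too, but on the two-arm reading Kruskal-Wallis still tests no interaction.

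A reader might strengthen the case by simulating an arm difference that is equal at all three visits. The design does not support this: T0 precedes treatment and the arms are randomised, so no systematic difference exists there. An effect that appears only after T0 would itself be an arm-by-visit interaction. The arm-effect figure above therefore uses T1 and T2 only.

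On the chi-square, the defence is largely right. The Hypothesis section states a null of equal effect, the tests are two-sided, and a general test of homogeneity fits both. It also does better when the effect is not monotone. What remains is that the stated research hypothesis and the planned proportions describe a shift to lower grades, which an order-using test serves somewhat better.

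A reader might also infer that the chi-square explains why the trial falls short of 80% power. It does not, since the rank test falls short as well. Nor are 0.618 and 0.535 chances of a lower grade; they include half the ties. The protocol names no event for its relative risk, but that is detail an unseen SAP may supply and it is not counted here.

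**Conclusion.** The interaction sentence is wrong as written. Kruskal-Wallis cannot test an interaction on any reading, and followed literally it can yield a false one. The rate is uncertain: about 13–23% or 80–92% for a common time change, and 57–72% for a constant arm effect after baseline. All of these depend on assumed shifts and a correlation that the protocol does not give. The direction of the error does not depend on them.

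The use of chi-square for the ordinal grade is not an error. Its 5% level is sound. The loss is about 6 points of power for the planned proportions, together with a less specific meaning when it is significant. These powers assume three grades, none in the high category, and grades read without error. A reader might infer that the primary test is invalid; nothing in the protocol supports that.

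**What to change.** In Statistical methods:

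1. Delete Kruskal-Wallis as the interaction test. If arm-by-visit is of interest, name the variables and fit an ordinal model with an arm-by-visit term that allows for repeated readings on one patient, such as a mixed proportional-odds model.
2. As a cheap improvement, make the primary between-arm comparison of the grade an ordinal one. This can be Mann-Whitney, which is Kruskal-Wallis in its proper two-group role, or a proportional-odds model. Keep the chi-square as a supporting test for any difference in pattern.

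The cost is a text edit, with power restated for whichever test is chosen. No extra samples are needed. There are two downsides. Power falls if the effect is not monotone (41% to 9% in the example). Proportional odds also holds only roughly for the planned proportions: the odds ratio is (0.35/0.65)/(0.15/0.85) = 3.05 at the 10^2 cut and (0.85/0.15)/(0.75/0.25) = 1.89 at the 10^3 cut, so a single odds ratio would be an average. Changing the test does not repair the sample size, which needs its own correction.

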## **2) Objectives:**

### **2.1. Aim of the study:**

This study will be conducted to evaluate the effectiveness of using dissolving Xylitol chewable tablets versus xylitol chewing gum with bedridden geriatric patients ,as an alternative to tooth brushing and mouth rinsing, in increasing salivary pH and decreasing bacterial count in both saliva and interdental plaque.

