##### **2) Eligibility criteria:**

###### **a- Eligibility criteria of participants :**

- **Inclusion Criteria :**

- (1) Age range above 65 years old
- (2) Bedridden patients
- (3) Males or females
- (4) Conscious patients
- (5) Co-operative patients approving to participate in the trial.
- (6) Subjects who signed informed consent

- **Exclusion criteria:**

- (1) Individuals had taken antibiotics during the last four weeks or anticipated doing so during the study
- (2) Subjects who wore removable prosthesis
- (3) Patients with systemic diseases that have any oral manifestations
- (4) History of Smoking
- (5) Allergy to any of chewing gum or tablets ingredients
- (6) Evidence of temporomandibular joint disorders
- (7) Presence of intraoral infections
- (8) Currently using any mouth rinse

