### **3) Interventions:**

In our study, we selected for both intervention and comparator, materials that don't need from those geriatric bedridden patients to leave their beds with both materials are xylitol containing materials but with different delivery system. The intervention is dissolving xylitol chewable tablets and the comparator is xylitol chewing gum.

The intervention is the newly introduced dissolving xylitol chewable tablets " Listerine Ready Tabs ". Technically, it's a rectangular-shaped, bilayer-compressed tablet that once chewed, creates just enough liquid to swish around your mouth to get a whole-mouth clean feeling. As manufacture claimed the tablet is easy to use just in three simple steps: chew (to activate), swish (to clean), then swallow as unlike mouthwashes which may contain alcohol and other ingredients not intended for ingestion, Listerine Ready Tabs are alcohol-free and safe to swallow which is highly suitable for bedridden patients. It's composed of Xylitol, Erythritol, Isomalt, Calcium Carbonate, Flavor, Magnesium Stearate, Cellulose Gum, Hydroxypropyl Cellulose, Tetrasodium Pyrophosphate, PVP, Sucralose, Acacia Senegal Gum, Potassium Acesulfame, Glycerin, and Potassium Sorbate. Moreover the beneficial effect of xylitol ,as mentioned before, the addition of Erythritol in its composition adds more value for the tablets as all studies strongly support the idea of erythritol as a caries-reducing dietary polyol with inhibitory effect on the growth of certain mutans streptococci isolates by a mechanism of growth inhibition differs from that caused by xylitol. Moreover, combinations of erythritol and xylitol will turn out to exert promising caries-limiting effects in humans as the combined effects may exceed or at least equal the separate effects of both polyols. (*Makinen, 2010*)

The comparator is Original Trident which is a soft gum sweetened with xylitol . It also contains sorbitol, Mannitol, Aspartame, Sucralose and Acesulfame potassium.

For our methodology, the saliva and the dental plaque samples will be collected along the previously determined timeline; **T0**: before taking either the intervention or the comparator and **T1**: immediately after 5min and **T2**: 15days (for salivary ph measurement and bacterial count in both saliva and interdental plaque).

- **For Intervention group:**

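### The aim is a fall in bacterial count and a rise in pH, but the outcomes are scored as the level found and the stated chi-square and t-test make no use of the T0 values collected from every participant

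*Protocol*

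**What the plan says.** - **Objective.** Protocol section 2.1 (Aim of the study) sets out to judge effectiveness "in increasing salivary pH and decreasing bacterial count in both saliva and interdental plaque". The research question (1.1) has the same direction. The sample size section gives, for each arm, the probabilities of the count being reduced to 10^2, 10^3 or 10^4.
- **Entry.** None of the six inclusion and eight exclusion criteria names a bacterial count or a pH. Patients already at the lowest grade can therefore enter.
- **Outcome.** Table 1 (Outcomes) grades the count from very low (10^2 cfu/ml) to high (10^5 cfu/ml). For its summary it says "Absolute risk will be reported for each intervention independently" and "Relative risk will be used to compare both interventions with 95 % CI". For pH it gives "Mean and Standard deviation". It has no change score, grade shift or reference to T0.
- **Analysis.** Statistical methods says "Comparisons between categorical variables will be performed using the chi square test", with a t-test for continuous data. It adds Kruskal-Wallis and two-way ANOVA for interactions whose variables it does not name.
- **T0 data.** The Interventions section has saliva and plaque taken at T0, "before taking either the intervention or the comparator", and again at T1 and T2. The participant timeline (Table 2) has outcomes assessed at all three.

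**The concern.** The aim and the sizing are worded as change, while the outcome scale and the stated tests are worded as level. Two patients show the gap. One is at 10^2 at T0 and at T2: nothing was reduced, yet the patient falls in the best grade. The other falls from 10^5 to 10^4: the count dropped tenfold, yet the patient lands in the second-worst grade of Table 1 and in the worst of the three cells used for sizing.

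The mismatch affects how well the result answers the stated aim, and how precise it is. The starting value is usually among the strongest predictors of the final one. Here it is measured in everyone and then not used in either stated comparison.

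**Working it through.** **1. The plan's own figure.** The sizing gives 29 for gum and 53 for tablets: 29 + 53 = 82. Adding 20% gives 82 × 1.2 = 98.4, stated as 98, or 49 per arm. The two components reproduce as chi-square calculations (2 degrees of freedom, alpha 0.05, power 80%) of each arm's three probabilities against an equal split:
- Gum: w = sqrt(3 × [(0.15 − 1/3)² + (0.60 − 1/3)² + (0.25 − 1/3)²]) = 0.579, n = 29.
- Tablets: w = sqrt(3 × [(0.35 − 1/3)² + (0.50 − 1/3)² + (0.15 − 1/3)²]) = 0.430, n = 53.

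No T0 value enters this calculation. Whether this is the right way to size a two-arm comparison is a separate matter. Only the 49 per arm is used below.

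**2. Chance imbalance in the share already at 10^2.** The Protocol does not give this share, p, so it is assumed. If the sizing cells are levels at follow-up, the gum arm has 15% at 10^2 in total. Gum patients who start and stay at 10^2 cannot then exceed 15%, so 5-15% is used as the range. With 49 per arm,

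SE = sqrt(2p(1 − p)/49)

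| Assumed p | SE of between-arm difference | Chance of a difference above 10 points |
|---|---|---|
| 5% | sqrt(0.095/49) = 4.4 points | about 2% |
| 15% | sqrt(0.255/49) = 7.2 points | about 17% |

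The planned difference in that cell is 0.35 − 0.15 = 20 points. An imbalance does not carry over in full, because other patients also reach 10^2. Even if every patient who starts at 10^2 stays there, a 10-point imbalance moves the outcome by between 10 × (1 − 0.35) = 6.5 and 10 × (1 − 0.15) = 8.5 points.

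**3. Precision from T0, for a continuous outcome only.** With T0-T2 correlation r (assumed; not in the Protocol), ANCOVA leaves a fraction 1 − r² of the variance:

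| Assumed r | Variance left | Variance removed | Equivalent multiple of patients, 1/(1 − r²) |
|---|---|---|---|
| 0.3 | 0.91 | 9% | 1.10 |
| 0.5 | 0.75 | 25% | 1.33 |
| 0.7 | 0.51 | 49% | 1.96 |

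This applies to pH, and to the count only if it is analysed as log10 CFU/ml. It does not give the gain for the four-grade outcome.

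**The case against.** **Randomization already deals with baseline differences.** This stands. A comparison of follow-up grades between randomized arms is unbiased, and the type I error of the chi-square test already allows for chance imbalance. The figures in step 2 describe ordinary sampling variation, not a flaw in validity.

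**The Protocol does not say that T0 is ignored.** This stands in part. The two-way ANOVA could have arm and visit as its factors, in which case T0 pH would enter. The factors are not named, though, and the ANOVA is for continuous data, so it does not reach the graded primary outcome. Kruskal-Wallis in its usual form compares groups on one factor and does not adjust for a starting value.

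**Covariate adjustment belongs in a statistical analysis plan.** Often it does, and one may exist. But the Protocol itself fixes the outcome scale, its summary and the tests, and these do not match its own aim and sizing language. That mismatch is in the document as it stands.

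**A reader might infer that a patient who is at 10^2 throughout is counted as a treatment success at each visit.** The text does not support this. It defines no success, does not say at which visit the tests are run, and words the sizing event as a reduction. What can be said is that such a patient falls in the best grade of Table 1.

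**Conclusion.** The point holds as one of precision and fit to the aim. The stated comparisons use the level found and not the T0 value, so they cannot separate a reduction from a low start, and they give up information already collected.

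The size rests on assumptions. With 5-15% of patients at 10^2 at T0, the standard error of the chance difference between arms is about 4.4-7.2 points at 49 per arm. With a T0-T2 correlation of 0.3-0.7, adjustment removes 9-49% of the variance for pH or log10 CFU.

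Four stronger readings are tempting and should not be drawn:
- **The comparison is biased.** It is not, given randomization.
- **Much larger starting shares, such as 30%, apply.** These exceed the 15% that the sizing gives for gum if its cells are levels.
- **Already-low patients dilute the planned 0.15 and 0.35.** If those probabilities are levels, such patients are already inside them and would be counted twice.
- **The lack of an entry level is a defect of its own.** Adjustment for T0 deals with it without any change to eligibility.

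This should be corrected, but it does not invalidate the trial.

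**What to change.** Amend Table 1 (Outcomes) and Statistical methods so that arms are compared at T2, adjusted for the participant's own T0 value, with all participants kept:
- **Count:** ordinal regression of T2 grade on arm and T0 grade, or ANCOVA of log10 CFU/ml on arm and T0 log10 CFU/ml. Name one of the two in advance.
- **pH:** ANCOVA of T2 pH on arm and T0 pH.
- **Any proportion described as a reduction:** define it against the participant's own T0 grade and report it only as a descriptive secondary summary. Those who start at the lowest grade cannot contribute, the remaining subset is of unknown size and has no sample size behind it, and a one-grade fall would score the same as a three-grade fall.

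The cost is protocol wording and slightly more analysis work. The T0 samples are already taken and cultured, so the adjusted comparison needs no screening, extra samples or added patients. If ordinal regression is chosen, the primary effect measure becomes an odds ratio. The absolute and relative risks in Table 1 can stay beside it as description.
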